9 STATISTICAL CONSIDERATIONS

9.1 Statistical Hypothesis

The primary study hypotheses are that L9LS will be safe and will confer protection against Pf infection. In the dose-escalation study, the primary objective is to evaluate the safety and tolerability. In the efficacy study, the primary objective is to evaluate the efficacy of L9LS compared to placebo.

Primary Endpoints:

• Part 1 and Part 2: Incidence and severity of local and systemic AEs occurring within 7 days after the administration of L9LS, and incidence of SAEs throughout the study period.

• Part 2: Pf blood-stage infection as detected by microscopic examination of thick blood smear for 52 weeks after administration of L9LS or placebo.

Secondary Endpoints:

Data from both parts of the study will be used to assess the following endpoints:

- Pf blood-stage infection as detected by microscopic examination of thick blood smear for 12 and 24 weeks after administration of L9LS or placebo
- Pf blood-stage infection as detected by RT-PCR for 24 and 52 weeks after administration of L9LS or placebo.
- Incidence of clinical malaria (definition 1, see section 2.2.2.3) for 24 and 52 weeks after administration of L9LS or placebo.
- Incidence of clinical malaria (definition 2, see section 2.2.2.3) for 24 and 52 weeks after administration of L9LS or placebo.
- To assess the primary objective and first four secondary objectives among children 5-17 months of age.
- To assess the primary objective and first four secondary objectives among children 18-59 months of age.
- Measurement of L9LS in sera of recipients.
- PK analysis of L9LS and the association of L9LS concentration with Pf infection risk.
- PK analysis of L9LS and the association of L9LS concentration with clinical malaria risk.

9.2 Sample Size Determination

9.2.1 Sample Size Considerations for the Dose-Escalation Study

The ability of the study to identify safety events can be expressed in terms of the probability of observing 1 or more event of interest (e.g., AEs) within each arm. With the sample size n=9 (receiving MAb) in each arm, there is over a 90% chance to observe at least 1 AE if the true rate is at least 0.226 and over a 90% chance to observe no AE if the true rate is no more than 0.011. Probabilities of observing 0 or more than 1 AE within a group are presented in Table 5 for a range of possible true event rates.

Table 5. Probability of events for different safety scenarios within an arm (n=9).

| True event | n=9 | | | | | |
|------------|--------------|-------|--|--|--|--|
| rate | Pr(0) Pr(>1) | | | | | |
| 0.005 | 0.956 | 0.001 | | | | |
| 0.01 | 0.914 | 0.003 | | | | |
| 0.02 | 0.834 | 0.013 | | | | |
| 0.035 | 0.726 | 0.037 | | | | |

| True event | n=9 Pr(0) Pr(>1) | | | | | |
|------------|------------------|-------|--|--|--|--|
| rate | | | | | | |
| 0.05 | 0.63 | 0.071 | | | | |
| 0.1 | 0.387 | 0.225 | | | | |
| 0.15 | 0.232 | 0.401 | | | | |
| 0.2 | 0.134 | 0.564 | | | | |
| 0.3 | 0.04 | 0.804 | | | | |

Abbreviations: Pr, probability.

9.2.2 Sample Size Considerations for the Efficacy Study

Table 6 shows initial sample size estimations powered to detect a 70% vaccine efficacy (1 – [proportion infected in L9LS/proportion infection in control]) at 12 months comparing L9LS at 10-20 mg/kg to placebo. Sample size calculations were done assuming the endpoint of any Pf infection will be calculated using a proportional analysis, 80% or 90% power, an alpha of 0.05, and that either 30%, 35%, or 40% of children in the placebo group are infected at 6 months and that 40% or 45% are infected at 12 months. (Time-to-event analyses typically require smaller sample sizes.) The primary endpoint will be at 12 months and will combine both MAb age groups who received two doses of L9LS and compare those subjects to the overall placebo group, i.e., we will assess MAb efficacy among children 5–59 months. However, the trial sample size is based on the secondary endpoint of 12-month MAb efficacy with two doses among the younger age group (5–17 months) versus the 5–17-month-old subjects in the placebo group, as these will require larger sample sizes than the primary endpoint. Factoring in 25% loss to followup over 12 months, and a doubling of the sample size in each intervention arm to allow for comparison of L9LS with a second dose (at 6 months) to placebo and comparison of L9LS without a second dose to placebo would require 108 children in each L9LS group and 54 children in the placebo arm, assuming 35% infected in the placebo group at 6 months.

Abbreviated Title: Anti-malaria MAb in Kenyan children

Version 6.0 Date: 2 Apr 2024

Table 6. Sample size calculations based on secondary 12-month endpoint, to achieve 80% power to detect efficacy of 70% at 6 months and 60% at 12 months, assuming 35% of the control group are infected by 6 months and 45% by 12 months.

| Arm | Assumed proportion infected in control group by 6 mos | mAb Efficacy at 6 months | Power | Number needed at 6 months | | Assumed % infected in control group by 12 mos | mAb Efficacy at 12 months | Number needed at 12 months | Number needed to enroll | Number with 20% LTFU* |
|------------------------------|---|-----------------------------------|----------|---------------------------------|-----|---|------------------------------------|-------------------------------------|-------------------------------|-----------------------|
| mAb 5-17 mos + Dose 2 | 0.30 | 70% | 80% | 50 | 120 | 0.40 | 60% | 52 | 104 | 130 |

| mAb 18 mos-5 years No dose 2 | 0.40 | 70% | 8070 | 33 | 00 | 0.45 | 60% | 43 | 80 | 108 | | |
| Placebo 5-17 mos | 0.40 | 70% | 80% | 35 | 44 | 0.45 | 60% | 43 | 43 | 54 | | |
| Placebo 18 mos-5 years | 0.40 | 70% | 80% | 35 | 44 | 0.45 | 60% | 43 | 43 | 54 | | |
| mAb 5-17 mos + Dose 2 | 0.40 | 700/ | 0.007 | 47 | 110 | 0.45 | 60% | 43 | 9.6 | 115 | | |
| mAb 5-17 mos No dose 2 | 0.40 | 70% | 90% | 47 | 118 | 0.45 | 60% | 43 | 86 | 115 | | |
| mAb 18 mos-5 years + Dose 2 | 0.40 | 700/ | 0.00/ | 47 | 118 | 0.45 | 60% | 43 | 86 | 115 | | |
| mAb 18 mos-5 years No dose 2 | 0.40 | 70% | 70% 90% | 7070 9070 |) 90% 4/ | 4/ 11 | 118 | 0.45 | 60% | 43 | 80 | 113 |
| Placebo 5-17 mos | 0.40 | 70% | 90% | 47 | 59 | 0.45 | 60% | 43 | 43 | 58 | | |
| Placebo 18 mos-5 years | 0.40 | 70% | 90% | 47 | 59 | 0.45 | 60% | 43 | 43 | 58 | | |
| | | | | | | | | | | | | |

Note: If infections in the control group are higher at 6 or 12 months than assumed but VE remains the same, then the statistical power increases.

^{*}LTFU = loss to follow up

9.3 Sample Size Considerations for the Year 2 Extension Study

In part 1b of the study for evaluating the safety of L9LS at 30mg/kg and 40mg/kg, 12 new participants will be enrolled into each age-dose group where 9 participants will receive L9LS of 30mg/kg (or 40mg/kg) and 3 will receive placebo. The probabilities of observing 0 or more than 1 AE among the L9LS recipients within a group are presented in Table 5 over a range of possible true event rates.

In year 2 extension study, safety endpoints will be assessed within each arm, and each L9LS arm will additionally be compared with the placebo arm. Table 7 presents the minimum detectable difference in adverse event rate with 80% and 90% power over possible event rates under placebo, with each arm of 108 participants.

Table 7. The minimum detectable difference in event rate between L9LS arm and placebo arm

| Event rate | With 80% p | ower | With 90% power | | |
|------------|-------------------|------------|----------------|------------|--|
| (under | Detectable | Event rate | Detectable | Event rate | |
| placebo) | difference (under | | difference | (under | |
| | L9LS) | | | L9LS) | |
| 0.05 | 0.119 | 0.169 | 0.143 | 0.193 | |
| 0.1 | 0.143 | 0.243 | 0.17 | 0.27 | |
| 0.2 | 0.172 | 0.372 | 0.201 | 0.401 | |
| 0.3 | 0.186 | 0.486 | 0.215 | 0.515 | |

In year 2 extension study to assess the protective efficacy, each L9LS arm will be compared with the placebo arm. Assuming a lost to follow up rate of 20%, Table 8 shows the comparison power at various rates of the infection with 108 participants per arm. In addition, the two L9LS arms will also be compared with each other, and the comparison power is shown in Table 9.

Table 8.The comparison power with 108 participants per arm and a lost to follow up rate of 20%

| Sample | Lost to | Infection rate | Infection rate | mAb | Power |
|----------|-----------|-----------------|----------------|----------|-------|
| size per | follow up | (under placebo) | (under L9LS) | efficacy | (%) |
| arm | rate | | | | |
| | (%) | | | | |
| 108 | 20% | | 0.225 | 0.5 | 89 |
| | | 0.45 | 0.18 | 0.6 | 97 |
| | | | 0.135 | 0.7 | 100 |
| | | | 0.2 | 0.5 | 82 |
| | | 0.4 | 0.16 | 0.6 | 95 |
| | | | 0.12 | 0.7 | 99 |
| | | | 0.175 | 0.5 | 75 |
| | | 0.35 | 0.14 | 0.6 | 90 |
| | | | 0.105 | 0.7 | 98 |

Table 9. The comparison power between two L9LS arms with 108 participants per arm and a lost to follow up rate of 20%

| Sample | Lost to | Infection rate | Infection rate in | Power |
|----------|-----------|----------------|-------------------|-------|
| size per | follow up | in the high | the low infection | (%) |
| arm | rate | infection arm | arm | |
| 108 | 20% | 0.15 | 0.05 | 59 |
| | | 0.15 | 0.1 | 17 |
| | | 0.2 | 0.05 | 85 |
| | | 0.2 | 0.1 | 45 |
| | | 0.2 | 0.15 | 14 |
| | | 0.25 | 0.05 | 96 |
| | | 0.25 | 0.1 | 74 |
| | | 0.25 | 0.15 | 37 |
| | | 0.25 | 0.2 | 12 |
| | | 0.3 | 0.05 | 99 |
| | | 0.3 | 0.1 | 91 |
| | | 0.3 | 0.15 | 66 |
| | | 0.3 | 0.2 | 33 |

9.4 Populations for Analyses

The following datasets will be considered in study analyses:

- Intention-to-treat (ITT) analysis dataset will include all subjects that are randomized and will be analyzed according to the initial randomization assignment.
- Modified intention-to-treat (MITT) analysis dataset will include all randomized subjects that receive the study intervention and will be analyzed according to the initial randomization assignment.
- Per-protocol (PP) analysis dataset will include all randomized subjects that receive the study intervention consistent with the initial randomization assignment and complete the scheduled visits, and will be analyzed according to the initial randomization assignment.
 In cases where subjects receive an intervention other than the one randomly assigned, an as-treated analysis will be additionally performed according to the actual product received.

9.4.1 Evaluable for toxicity

All participants will be evaluable for toxicity from the time of their first treatment with L9LS or placebo. The toxicity analysis will be MITT.

9.4.2 Evaluable for objective response

Not applicable.

9.4.3 Evaluable Non-Target Disease Response

Not applicable.

9.5 Statistical Analyses

A detailed study statistical analytical plan for the final analysis, which will supersede the study protocol, will be drawn up during the study before the unblinding of data at database lock.

9.5.1 General Approach

In general, descriptive statistics will be tabulated by treatment arm for endpoints of interest. This will include point estimates (mean, geometric mean, median, or proportions) and their respective 95% confidence intervals. Formal comparisons will use standard methods, contingency tables for categorical variables, t-tests for comparing means if data follow a normal distribution or geometric means if data after log transformation follow a normal distribution, or nonparametric analogs for comparing medians. Unless specified in the subsequent sections, comparisons will be two-sided with type I error rate of 0.05.

Missing data will be considered as "missing completely at random" provided the amount of missing data is modest (e.g., <10%). We will examine the "missing completely at random"

assumption if the amount of missing data is more than 10%. If the assumption does not hold, missing data will be handled under the "missing at random" assumption (that is, missingness depends only on observed variables) via methods such as multiple imputation and inverse propensity weighting. To handle the possibility of "missing not at random," a sensitivity analysis will be performed by imputing missing binary observations with the observed proportion in the opposite arm. A secondary sensitivity analysis will be considered by imputing missing binary observations as failures.

Randomization: In the efficacy study, participants will be stratified by age (5-17 months versus 18-59 months) and then each age group will be randomized **2:1** to the L9LS arm and the placebo arm. The total number of participants will be 108 in each arm. In the dose-escalation study, participants in each age group, starting with 5-10 years, followed by 5-59 months, will be recruited and randomized 3:1 to receive L9LS at the dose of 5 mg/kg or placebo; if no safety concerns arise, randomization into the L9LS at the dose of 10 mg/kg or placebo, and finally 20 mg/kg or placebo, ensues in the same manner. To limit the number of dropouts before L9LS administration, randomization and L9LS administration will occur as close in time as possible.

9.5.2 Analysis of the Primary Endpoints

Analysis for the primary endpoint for safety and tolerability is described in section 9.5.5.

Analysis for the primary efficacy endpoint, protective efficacy with Pf infection determined by blood smear, is described in section 9.5.4.

9.5.3 Analysis of the Secondary Endpoint(s)

Analysis of the secondary efficacy endpoints, for example, incidence of Pf infection determined by RT-PCR and incidence of Pf infection against clinical malaria, is described in section 9.5.4.

Analyses of the secondary endpoints for the PK of L9LS and the association of L9LS concentration with Pf infection risk are described in section 9.5.6.

9.5.4 Efficacy Analyses

The primary efficacy endpoint (efficacy study primary endpoint) is the incidence of malaria infection defined as blood smear—positive Pf infection, starting on Day 7 after MAb/placebo administration, through 52 weeks after administration. The secondary efficacy endpoints are the incidence of malaria infection as determined by RT-PCR and the incidence of clinical malaria, up to 12, 24 weeks and up to 52 weeks, as well as the incidence of malaria infection by blood smear up to 12 and up to 24 weeks. The efficacy analyses will be MITT over participants in the efficacy study.

The primary efficacy analysis will be based on time to the first infection. The survival patterns will be described by Kaplan-Meier curves for each arm and compared by the logrank test across different arms. The protective efficacy of the study product will be estimated by the hazard ratio from the Cox proportional hazards model. These analyses will be carried out by R packages or commands in similar statistical software that account for interval censoring: package "interval" for deriving a nonparametric maximum likelihood estimation based on the Kaplan-Meier survival curve and logrank test, and package "icenReg" for Cox proportional hazards regression. To address the heterogeneity of the study population, a Cox regression with regressors other than the study arm will be additionally performed to account for potential differences among participants. The regressors will include time of enrollment and possibly those covariates that are significantly different between the study product arms and the placebo arm in spite of randomization. The primary analysis will compare all children (both age groups) receiving MAb to placebo. Secondary endpoint analyses will compare the younger children receiving MAb to the younger children in the placebo group and the older children receiving MAb to the older children in the placebo group. Since these are secondary endpoints, no adjustments for multiple comparisons will be made.

The secondary efficacy analysis will be based on the proportion of infection. The proportion of infection will be estimated for each arm and compared across arms based on Kaplan-Meier estimates: the proportion of infection by one minus the Kaplan-Meier estimate in the arm, and the vaccine efficacy by one minus the relative risk of infection with melding method for constructing the melded 95% confidence interval of the vaccine efficacy. 34

Finally, all clinical malaria episodes will be included in exploratory analyses. All person-time during the trial, including the time after the initial positive evaluation for Pf infection or clinical malaria, will be included in these analyses. This approach will use a counting process which is an extension of the Cox proportional hazards model to incorporate multiple events. 35 The 14 days following treatment with artemether-lumefantrine will be removed from these analysis. In these models the number of prior events will be included as a covariate in order to ensure that the conditional independence assumption of the counting process is still met since a previous infection may confer some future protection. 36

Although the trial will not be weight-stratified, given that we have age stratification, we anticipate that participants will cover the dose range from 10 mg/kg to 20 mg/kg in the efficacy analyses. In addition to the above efficacy analyses that compare each dose arm with the placebo arm, an exploratory analysis will be additionally conducted to assess how dosage, in terms of mg of L9LS per kg of subject body weight, affects the protective efficacy.

Making these data available in a timely manner will add to the evidence base needed to plan a potential phase 3 trial of L9LS in settings with seasonal malaria transmission.

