Part 2 extension: Assuming there are no safety signals from the day 7 review following dosing children with 30 and 40 mg/kg of product, and prior to the last study visit of the original protocol described above (September 2022 to June 2024), study participants who remain enrolled in the part 2 efficacy study will be invited to participate in a 12-month extension of the study. A separate written consent process will take place. Enrolled children will continue in the same study groups as in part 2: 1 dose L9LS, 2 doses L9LS, or placebo. A dose (of L9LS or placebo) will be given at the start of the extension and again after six months. Those receiving L9LS will receive a dose between 20 and 40 mg/kg, still in a double-blinded fashion. The monthly visit and sample collection schedule will mirror that in part 2.

Objectives:

Primary Objectives:

Part 1:

1. Safety: To evaluate the safety and tolerability of L9LS administered at doses of 5 mg/kg, 10 mg/kg, and 20 mg/kg by SC administration to healthy Kenyan children.

Part 1b:

1. Safety: To evaluate the safety and tolerability of L9LS administered at doses of 30 mg/kg and 40 mg/kg by SC administration to healthy Kenyan children

Part 2:

1. Safety: To evaluate the safety and tolerability of L9LS administered at doses of 10-20 mg/kg by SC administration to healthy Kenyan children.

2. Efficacy: To assess the efficacy of two doses of L9LS at a concentration of 10-20 mg/kg, administered SC to participants aged 5-59 months of age against first/only Pf malaria infection diagnosed by blood smear microscopy (irrespective of fever) over 12 months compared to placebo.

Secondary Objectives:

- 1. To assess the efficacy of one dose of L9LS at 10-20 mg/kg against first/only Pf malaria infection diagnosed by blood smear microscopy over 3 and 6 months compared to placebo.
- 2. To assess the efficacy of one dose of L9LS at 10-20 mg/kg against first/only Pf malaria infection diagnosed by blood smear microscopy over 12 months compared to placebo.
- 3. To evaluate the efficacy of L9LS at 10-20 mg/kg against first/only Pf malaria infection as detected by PCR over 3, 6 and 12 months compared to placebo.
- 4. To assess protection of L9LS at 10-20 mg/kg against clinical malaria (first/only and all episodes) at 3, 6 and 12 months compared to a placebo.
- 5. To assess the primary objective and secondary objectives 1-4 among children 5-17 months of age.

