Safety outcomes will be evaluated within arms to assess the safety of a third and fourth L9LS dose vs. placebo in year 2 (1 vs. 3 and 2 vs. 3). Finally, safety outcomes of L9LS vs. placebo will be evaluated in aggregate (1 + 2 vs. 3).

PK of L9LS will be evaluated throughout the study for those receiving various numbers of L9LS doses. The presence of ADA to L9LS will be assessed in sera of recipients at specific timepoints throughout the study and will be correlated with L9LS PK.

In exploratory analysis, L9LS serum concentration will be correlated with the risk of Pf infection (assessed by blood smear and RT-PCR) and clinical malaria. The protective efficacy of L9LS against *P. falciparum* infection (by blood smear and RT-PCR) and clinical malaria will be assessed by comparing: 1) arm 1 vs. arm 3 (over 12 months); 2) arm 2 vs. arm 3 (over 12 months); arms 1+2 vs. arm 3 (over 6 months); and arm 1 vs. 2 (over 12 months).

Study site

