In the ongoing phase 2 trial of L9LS in Mali involving healthy children aged 6-10 years, a prespecified exploratory analysis of the relationship between the weight-based dose of L9LS (mg of L9LS administered per kg of body weight) and protective efficacy suggested that ~12 mg/kg of L9LS corresponds to a protective efficacy against clinical malaria of approximately 75% over six months compared to placebo. In addition, preliminary PK analysis indicates that the average half-life of L9LS in Malian children is ~35 days, compared to ~55 days in Malian adults, and ~65 days in U.S. adults. After receiving 10-20 mg/kg of L9LS, the average number of days required for the serum concentration of L9LS to fall below the lower limit of detection (0.61 μg/mL) was 243 (95% CI 232–254). Therefore, we anticipate that a single dose of L9LS in the range of 10-20 mg/kg will not provide high-level protection (>75%) against malaria over 12 months in healthy Kenyan children 5-59 months of age who are exposed to intense perennial malaria transmission. Therefore, the 1-year extension of the phase 2 Kenya trial will assess the safety and protective efficacy of L9LS at a dose range of 20-40 mg/kg.

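### A single 52-week Cox hazard ratio would blur the waning of one dose; the plan needs a placebo-controlled estimate for weeks 24 to 52

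*Combined protocol and SAP*

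**What the plan says.** Section 9.5.4 bases the primary efficacy analysis on time to first blood-smear infection, "starting on Day 7 after MAb/placebo administration, through 52 weeks after administration". It compares arms by the log-rank test and states: "The protective efficacy of the study product will be estimated by the hazard ratio from the Cox proportional hazards model". Section 9.5.3 refers the secondary efficacy endpoints to the same section. Secondary objective 2 in section 1.1 is "To assess the efficacy of one dose of L9LS at 10-20 mg/kg against first/only Pf malaria infection diagnosed by blood smear microscopy over 12 months", against placebo; objectives 5 and 6 repeat it by age group.

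Other analyses are planned as well. Section 9.5.4 includes Kaplan-Meier curves by arm, a secondary analysis giving "vaccine efficacy by one minus the relative risk of infection with melding method", and "the incidence of malaria infection by blood smear up to 12 and up to 24 weeks". Section 9.5.6 models infection risk on L9LS concentration among L9LS recipients. Section 9.5.11 compares one with two doses as an exploratory analysis.

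On waning, section 4.2.2 gives an average half-life of about 35 days in Malian children and a mean of 243 days to fall below detection after 10-20 mg/kg. It concludes that "a single dose of L9LS in the range of 10-20 mg/kg will not provide high-level protection (>75%) against malaria over 12 months". The plan specifies no check of proportional hazards, no time-varying arm effect and no estimate for weeks 24 to 52.

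**The concern.** A Cox hazard ratio describes a treatment effect well when the effect is roughly constant. The protocol's own pharmacokinetics make that unlikely for one dose followed for a year. The 52-week hazard ratio then averages an early strong effect with a later weak one. The weights depend on when infections occur and on how fast each arm's risk set empties. The result can look like moderate year-long protection when the protection lies almost wholly in the first half.

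This matters because section 2.2 says that a year of protection from a single dose has important implications for feasibility, acceptability and cost. Whether one dose still protects in months 6 to 12 is therefore a question the trial should answer directly.

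**Working it through.** **Reproducing the plan's figure.** Table 6 is built "assuming 35% of the control group are infected by 6 months and 45% by 12 months", with efficacy (one minus relative risk) of 70% and 60%. With unpooled variance, two-sided alpha 0.05 and 80% power, n = (1.960 + 0.842)² × [p0(1−p0) + p1(1−p1)] / (p0−p1)².
- 6 months, 0.35 v 0.105: 7.849 × (0.2275 + 0.0940) / 0.0600 = 42.0, so 43.
- 12 months, 0.45 v 0.18: 7.849 × (0.2475 + 0.1476) / 0.0729 = 42.5, so 43.

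Both match the table. The same inputs already imply non-proportional hazards:
- Months 0-6: 1 − ln(0.895)/ln(0.65) = 74% hazard efficacy.
- Months 6-12: 1 − ln(0.82/0.895)/ln(0.55/0.65) = 48%.

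**Inputs for the projection.**
- Early hazard efficacy of 66% and 70%, from the six-month time-to-event results for 150 mg and 300 mg in Malian children (section 2.2.1.3).
- Efficacy after week 24: 0%. This is an assumption; the documents give no figure.
- Control infection of 35% by 6 months and 45% by 12 months (Table 6). The alternative is 66.7% per six months, from the placebo arm of another trial at the site (section 4.1), taken at constant hazard, which is also an assumption.

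**Placebo cumulative hazards.**
- Table 6: −ln(0.65) = 0.431 to week 24, then ln(0.65/0.55) = 0.167.
- Site rate: −ln(0.333) = 1.100 over Day 7-168, then 1.100 × 196/161 = 1.339 over Day 168-364. The 52-week placebo risk is 1 − exp(−2.438) = 91.3%.

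**Cox limit.** With 1:1 arms and no drop-out, the large-sample log hazard ratio b solves ∫[Y1h1 − (Y1h1 + Y0h0) · Y1e^b/(Y0 + Y1e^b)]dt = 0. Here Y is the fraction still uninfected and h the hazard, with subscript 1 for L9LS and 0 for placebo. Solved numerically, as 1 − e^b:

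| Control infection | Early 66%, late 0% | Early 70%, late 0% |
|---|---|---|
| 35% / 45% | 50% | 53% |
| 66.7% per six months, constant hazard | 45% | 48% |

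A grouped likelihood on the monthly visits, which mimics the planned interval-censored fit, agrees to within 0.1 percentage point.

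**Hand check on the weighting (early 70%).** The plain ratio of cumulative hazards gives 1 − (0.3 × 0.431 + 0.167)/0.598 = 50% at Table 6 rates and 1 − (0.3 × 1.100 + 1.339)/2.438 = 32% at the site rate. Cox gives 53% and 48%. The excess arises because the risk sets shrink and early events gain weight.

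**Planned cumulative measure (early 70%).**
- Table 6: treated risk 1 − exp(−0.296) = 25.6%, so 1 − 0.256/0.45 = 43%.
- Site rate: treated risk 1 − exp(−1.669) = 81.2%, so 1 − 0.812/0.913 = 11%.

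**Sensitivity.**
- Cox efficacy runs from 36% to 66% over early efficacies of 66%, 70% and 75% and control patterns of 30/40, 35/45, 40/45, constant 35% and constant 66.7% per six months.
- With 20% late efficacy, 70% early and Table 6 rates, Cox reads 58%.
- A smooth concentration-effect curve, using the 35-day half-life and calibrated to 66-70% at six months, gives Cox 53-56% at Table 6 rates, with 9-11% average efficacy in months 6-12.

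**The case against.** The strongest reply is that the hazard ratio is not the only efficacy measure. Kaplan-Meier curves, one minus relative risk and the 12- and 24-week horizons would all show a fall, and section 9.5 promises a superseding analysis plan. This stands in part. The decline would be partly visible, but none of these gives months 6-12 efficacy against placebo with an interval. The 52-week cumulative figure still contains the early effect, and the concentration model uses L9LS recipients only.

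A reader might infer that the Cox figure is wrong and that cumulative efficacy should replace it. The numbers do not support that. Between the two control scenarios cumulative efficacy moves from 43% to 11%, while Cox moves from 53% to 48%. A product with a constant 70% hazard reduction and no waning would give cumulative efficacy of 1 − (1 − exp(−0.3 × 0.598))/0.45 = 64% at Table 6 rates, but only 1 − (1 − exp(−0.3 × 2.438))/0.913 = 43% at the site rate. Much of a low cumulative figure can therefore be saturation of first infections. The two measures answer different questions.

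A reader might also infer that one dose is shown to do nothing after month 6. It is not. Day 243 is about week 35, 11 weeks after the cut, and the pharmacokinetics come from Malian children, not from this trial. Nor does the problem require most placebo children to be infected early: Table 6 assumes 35% by six months. What matters there is that 35 of every 45 control infections fall in the first half.

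**Conclusion.** The point holds for the 12-month comparison of one dose with placebo. Under the stated assumption of no effect after week 24, the single 52-week hazard ratio would still read about 50-53% at the main Table 6 control rates and 45-48% at the site rate. These are projections, not document figures, and they depend on the timing of control infections and on early efficacy.

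Two wider readings are not supported. The primary objective compares two doses with placebo, and the second dose at month 6 makes that comparison much less sensitive to this problem. Extension arm 2 versus arm 3 is exploratory and uses 20-40 mg/kg, whereas the day-243 figure relates to 10-20 mg/kg, so the sizes above should not be carried over to it. This is a worthwhile improvement to a secondary analysis, not a fault in the primary one.

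**What to change.** In section 9.5.4 or the superseding analysis plan, before unblinding:
- For 12-month comparisons of one dose with placebo (secondary objective 2 and its age-group versions), add an arm-by-period term cut at Day 168. Report the hazard ratio with 95% interval for Day 7 to week 24 and for weeks 24 to 52.
- Label the 52-week hazard ratio as a time-averaged effect. Report the already planned 52-week one-minus-Kaplan-Meier efficacy with its melded interval beside it, not in place of it.
- Show the same split for two doses and, as exploratory, for extension arm 2 versus arm 3.
- Leave the log-rank test and the two-dose primary analysis unchanged.

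The cost is some wording and one model term, with no new data or participants. Each half-year estimate will have a wider interval. The weeks 24-52 estimate conditions on children still uninfected at week 24, so it is not a purely randomised comparison and should be labelled so.
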